3. STUDY OBJECTIVES

3.1 Primary Objectives

The primary objectives of this study are:

- To assess the safety and tolerability of XP-8121 after once-weekly SC injections in adult subjects with hypothyroidism
- To determine a target dose conversion factor from stably dosed oral levothyroxine to XP-8121 in subjects with hypothyroidism

3.2 Secondary Objectives

Secondary objectives of this study are:

- To determine a dose range of XP-8121 capable of maintaining normalized TSH following a switch from stable replacement therapy with oral levothyroxine
- To evaluate a safe initiation dose of XP-8121 based on the prior stable dose of oral levothyroxine
- To evaluate a safe titration scheme for dosing XP-8121 to TSH target

3.3 Exploratory Objectives

Exploratory objectives of this study are:

- To characterize the dynamics of thyroid hormones and TSH in blood during and after titration (i.e., Titration and Maintenance Periods) with XP-8121
- To characterize the PK of plasma thyroid hormones following multiple once-weekly XP-8121 SC injections in adult subjects with hypothyroidism

- To compare subject treatment satisfaction between daily oral levothyroxine and once-weekly XP-8121 SC injections

4. STUDY DESIGN

4.1 General Design

Only a synopsis of the study is presented herein, full details can be found in the protocol. This is a non-randomized, open-label, single arm, self-controlled study of XP-8121 to determine a target dose conversion factor from stably dosed oral levothyroxine to XP-8121 in subjects with hypothyroidism and to assess the safety and tolerability of XP-8121 after once-weekly SC injections.

This study includes the following periods: Screening, Titration Period, and Maintenance Period. The study will conclude with an End of Maintenance or Early Termination (ET) Visit. The XP-8121 initiation dose will correspond to 50% of the target weekly dose of XP-8121 SC (in μ g), which is calculated as the current daily oral levothyroxine dose multiplied by 4, rounded up to the nearest 50 μ g.

During the Titration Period, subjects will come into the clinic once a week for at least 2 and up to 8 weeks, as applicable, for dosing administration. Based on free thyroxine (fT4) levels, XP-8121 will be titrated biweekly (every other week) by intervals of 25% of the target dose. TSH and T4 (free and total) will be checked weekly. A safety check will be completed 72 hr. (\pm 1 day) after the initial dose and each escalation during the Titration Period. If fT4 exceeds the upper limit of normal during titration, the XP-8121 dosage will be lowered and held at the previously tolerated dose.

[figure not shown]
Once subjects have completed the Titration Period, they will continue at the same dose of XP-8121 in the Maintenance Period for 4 weeks, returning to the Clinical Research Unit (CRU) on a weekly basis for dosing. An End of Maintenance Visit will be performed at Day 29 (1 week after the last XP-8121 dose). Subjects not achieving an adequate fT4 at \leq 125% of the target dose or the maximum weekly dose of 1500 μ g may also continue into the Maintenance Period at the discretion of the Investigator and after conferring with the Medical Monitor. Titration details are outlined in Appendix A of the study protocol.

Subjects completing the Maintenance Period will have been maintained on a stable dose of XP-8121 for a total of approximately 6 weeks: subjects are required to be on a stable dose of XP-8121 for the last 2 weeks of the Titration Period, enter the Maintenance Period on the same dose, and continue at the same dose during the 4-week duration of the Maintenance Period. During Week 4 of the Maintenance Period, a subgroup of subjects (~12) who have been on a stable dose of Synthroid for at least 3 months prior to Screening and who have maintained adequate trough fT4 and total T4 levels in the Maintenance Period will participate in a PK sub-study. Subjects will be housed in the CRU for 9 days and 8 nights to undergo PK sample collections at specified timepoints as outlined in the study protocol.

After completing the Maintenance Period, subjects will complete the study with an End of Maintenance Visit and will subsequently restart their previous daily levothyroxine PO dose. AEs (Adverse Events) that are ongoing at the End of Maintenance Visit will be recorded on the case report form (CRF) and followed until resolution or maximally up to 14 days after the End of Maintenance Visit or ET Visit. Subjects that withdraw or are discontinued will have an ET Visit 14 days (\pm 2 days) after the last dose of XP-8121. Subjects who withdraw or are discontinued, for any reason, will not be replaced.

Approximately 44 subjects who meet all inclusion criteria and exclusion criteria will be enrolled. Approximately 12 subjects will be enrolled in the PK sub-study.

Figure 1: Study Design Schema

a: Titration details are outlined in Appendix A of the study protocol.

b: A subgroup of subjects (~12), who have been on Synthroid for at least 3 months prior to Screening and who have maintained adequate trough T4 (free and total) levels in the Maintenance Period will participate in a PK sub-study. During Week 4 of the Maintenance Period, subjects will be housed in the CRU for 9 days and 8 nights to undergo PK sample collections at specified timelines as outlined in the study protocol.

4.2 Randomization and Treatment Assignments

All enrolled subjects will receive XP-8121 with titrated dosage; randomization is not applicable.

4.3 Blinding/Unblinding

This study is open-label: subjects, investigators, and study staff are aware of treatment identity.

4.4 Sample Size Considerations

Assuming a between-subject coefficient of variation of 0.5 and a within-subject, between-measurements correlation of 0.5, a sample size of 38 subjects will have 80% power to reject the null hypothesis that the dose conversion factor is less than 3.2X or more than 5X, in favor of the alternative hypothesis that the dose conversion factor is between 3.2X and 5X (in other words, within 80% and 125% of the proposed 4X conversion factor derived from Population PK modeling). For the exploratory endpoint of the treatment satisfaction questionnaire for medication (TSQM-9), assuming a SD of differences of 20, a sample size of 34 subjects will have 80% power to detect a difference of 10 in means (domain scores range from 0 to 100) with a 5% two-sided significance level ($\alpha=0.05$). Taking into consideration non-completers and non-normalizers of TSH at study end, a total of 44 subjects will be enrolled.

5. CHANGES IN THE ANALYSES SPECIFIED IN THE PROTOCOL

Dose-normalized PK parameters have been removed as endpoints.

6. STUDY ENDPOINTS

6.1 Schedule of Assessments

The assessments planned to be collected at each visit are presented in the study protocol.

6.2 Timepoint Definitions

6.2.1 Relative Day

The date on which the first dose of study drug was administered will be considered as relative day 1, while the day before that will be relative day -1 (there is no relative day 0). Relative days will be calculated using the following formula only if the date of the assessment is fully known (i.e., the relative day will be missing if the assessment date is a partial date):

Relative Day = Date of Assessment – Date of First Dose of Study Drug (+1 if Date of Assessment ≥ Date of First Dose of Study Drug).

6.2.2 Visit and Timepoint Windows

Nominal, scheduled visits and timepoints will be used for analysis. Unscheduled visits will be considered for clinically significant or abnormal safety summaries. Scheduled and unscheduled visits will be listed.

6.2.3 Baseline

Two baselines are defined for this study as the last evaluable measurement taken prior to the date/time of the first dose of study drug administration in the Titration Period (prior to any dose of study treatment) and prior to the date/time of the first dose of study drug administration in the Maintenance Period. For electrocardiograms, if a cardiologist interpretation is available on this record, this value will be used as baseline for the appropriate period.

Vital signs (blood pressure, heart rate) baseline will use the average of the triplicate assessments in the last timepoint occurring prior to the first dose of study drug treatment administration for each treatment period.

All change from baseline analyses will use the Titration Period baseline across all records in addition to the Maintenance Period baseline on records only from the Maintenance Period, as applicable.

6.3 Protocol Deviations

Protocol deviations will be documented in the clinical database for subject-specific protocol deviations and the ProSciento Clinical trial Management System (CTMS) for site- and study-specific protocol deviations. The protocol deviations will be reviewed according to the Protocol Deviation Plan. Before database lock; this review will include a confirmation of which deviations are considered to be major. The following representatives from Xeris will participate in the review of the deviations: Biometrics, Clinical Research Operations, Regulatory, Quality and Medical. The database will not be locked until the deviations are finalized.

6.4 Demographics and Baseline Characteristics

The following assessments will be collected at baseline:

- Demographic parameters
 - Age (years) – calculated as: *(Date of Informed Consent – Date of Birth)/365.25*
 - Sex
 - Race
 - Ethnicity

- Vital Signs
 - Weight (kilograms [kg])
 - Height (centimeters [cm])
 - Body Mass Index (BMI; kg/m²) – calculated using the following formula: *Weight (kg) ÷ (Height (cm)/100)²*
- Medical History
 - Coded using MedDRA version 26.0
- Disease History
 - Hypothyroidism History Type (e.g., Primary, Secondary, Tertiary)
 - Prior Oral Levothyroxine Brand and Dose

6.5 Prior and Concomitant Therapies

The World Health Organization (WHO) Drug Dictionary version from March 2023 will be used to code the recorded medications to Anatomical Therapeutic Chemical (ATC) level 2 and standardized (generic) medication name.

Prior medications include any recorded medication that was taken and discontinued before the date/time of first dose of study drug administration. Concomitant medications include any recorded medication that was taken on/after the date/time of first dose of study drug administration. See [Section 8.3](#) below for details on how to identify prior vs. concomitant when the start/end dates for the medication usage are partial dates or missing.

6.6 Primary Endpoints

The primary endpoints are as follows:

- Safety endpoints collectively include incidence, frequency, severity, and relationship to study drug of Treatment-Emergent Adverse Events (TEAEs), including clinically significant vital sign measurements, safety laboratory test results, Electrocardiograms (ECGs), and physical examinations.
 - Described in [Section 6.9](#).
- Tolerability assessments include Modified Draize Scale and Injection Site Discomfort questionnaires.
 - Described in [Section 6.9.7](#).
- Geometric mean ratio of the weekly dose of XP-8121 SC (in µg) to the daily dose of oral levothyroxine (i.e., dose conversion factor) as recorded in the concomitant medications electronic case report form (eCRF), and where the XP-8121 dose corresponds to the administration immediately preceding collection of blood TSH used to determine normalization at the end of the Maintenance Period.
 - The final dose conversion factor will be assessed by comparing the In-transformed final XP-8121 dose that maintains normalized TSH at the end of Maintenance Period to the In-transformed daily oral levothyroxine dose the subject was taking before the study. The dosage for oral levothyroxine and XP-8121 should use micrograms as a unit. This primary endpoint will be assessed using the Completer population (as defined in Section 7) for subjects with primary hypothyroidism only (see Section 9.5 for sensitivity analyses on other populations/subsets).

6.7 Secondary Endpoints

The secondary endpoints are as follows (only subjects with primary hypothyroidism will be considered for the secondary endpoints):

Endpoint	Applicable to	Timespan	Derivation
Normalized Values	TSH	Throughout the Maintenance Period	Normalized TSH will be defined as values of TSH within the normal range throughout the Maintenance Period
Normalized Values	TSH	End of Maintenance Period	Normalized TSH will be defined as values of TSH within the normal range at the end of the Maintenance Period
Observed Values that are lower than, within, or higher than the normal range	Total thyroxine (T4) fT4 TSH	During the Titration and Maintenance Periods	Observed results at each visit will be compared to the normal range and subjects will be categorized as "Low", "Normal", or "High".

6.8 Exploratory Endpoints

Exploratory endpoints are as follows (only subjects with primary hypothyroidism will be considered for the non-PK exploratory endpoints):

Endpoint	Applicable to	Timespan	Derivation
Observed Values	T4 fT4 TSH	Titration Period Maintenance Period	N/A
Change from Baseline	T4 fT4 TSH	Titration Period Maintenance Period	Value at Timepoint – Value at applicable Baseline Maintenance Period records will also display change from Titration Period Baseline
Time of Maximum Concentration (t_{max}) (hours)	T4 Triiodo-thyronine (T3)	168-hr PK Period for Subjects in PK sub-study	Time in hours of the Maximum Value
Maximum Concentration (C_{max}) (ng/mL)	T4 T3	168-hr PK Period for Subjects in PK sub-study	Maximum concentration
Minimum Concentration (C_{min}) (ng/mL)	T4 T3	168-hr PK Period for Subjects in PK sub-study	Minimum concentration

Endpoint	Applicable to	Timespan	Derivation
Last concentration (C_{trough}) (ng/mL)	T4 T3	168-hr PK Period for Subjects in PK sub-study	Concentration at 168hrs
Mean concentration at steady state (C_{ss})	T4 T3	168-hr PK Period for Subjects in PK sub-study	Calculated as $\text{AUC}_{0-168\text{hrs}} / 168\text{hrs}$
$\text{AUC}_{0-168\text{hrs}}$	T4 T3	168-hr PK Period for Subjects in PK sub-study	
AUC using the observed result over a dosing interval using the “linear-up log-down” approach, which uses the linear trapezoidal method up to time t_{max} and the logarithmic trapezoidal method for all times after t_{max}.
 
The linear trapezoidal method is defined as the sum across all adjacent pairs of timepoints:
 $\frac{1}{2}(t_{i+1} - t_i)(\text{concentration}_{i+1} + \text{concentration}_i)$ 
Where t_i and t_{i+1} are adjacent collection timepoints, and concentration_i and $\text{concentration}_{i+1}$ are the respective concentration levels at those times.
 
The logarithmic trapezoidal method is defined as the sum across all adjacent pairs of timepoints:
 $\frac{(t_{i+1} - t_i)(\text{concentration}_i - \text{concentration}_{i+1})}{\ln(\text{concentration}_i) - \ln(\text{concentration}_{i+1})}$ 
Where t_i, t_{i+1}, concentration_i, and $\text{concentration}_{i+1}$ are the same as described above.
 
The time 0 value will use the nominal time of collection at time 0 while actual time elapsed will be used for timepoint >0.

Observed Values	Convenience Domain Score of the Treatment Satisfaction Questionnaire for Medication (TSQM-9)	Per collection timepoint	
Convenience Score is the transformed total of items 4, 5, and 6 as follows:
 
If all items are non-missing: $([\{\text{Sum of Item 4 to Item 6}\} - 3] \text{ divided by } 18) * 100$.
 
If one item is missing: $([\{\text{Sum of non-missing items 4, 5, and 6}\} - 2] \text{ divided by } 12) * 100$.
 
If two or more items are missing, then do not calculate.

Endpoint	Applicable to	Timespan	Derivation
Observed Values	Overall Satisfaction Domain Score of TSQM-9	Per collection timepoint	
Overall Satisfaction is the total of Item 7, 8, and 9.
 
If all items are non-missing: $([\{ \text{Sum of Item 7 to Item 9} \} - 3] \text{ divided by } 14) * 100$.
 
If item 7 or 8 is missing: $([\{ \text{Sum of non-missing Item 7 to Item 9} \} - 2] \text{ divided by } 10) * 100$.
 
If item 9 is missing: $([\{ \text{Sum of item 7 and item 8} \} - 2] \text{ divided by } 8) * 100$
 
If two or more items are missing, then do not calculate.

Observed Values	Effectiveness Domain Score of TSQM-9	Per collection timepoint	
Effectiveness is the total of Items 1, 2, and 3.
 
If all items are non-missing: $([\{ \text{Sum of Item 1 to Item 3} \} - 3] \text{ divided by } 18) * 100$.
 
If one item is missing: $([\{ \text{Sum of non-missing Item 1 to Item 3} \} - 2] \text{ divided by } 12) * 100$.
 
If two or more items are missing, then do not calculate.

Observed Values	Subject Preference Survey	Per collection timepoint	N/A

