**Table 5: Pharmacokinetic Sample Timepoints**

XP-8121 Pharmacokinetic Sampling	
Day 22: Predose	within 10 minutes of dosing
Day 22: 1, 6, 12, and 18 hr post dose	±5 minutes for 1-hour timepoint; ±10 minutes for 6, 12, and 18 hr timepoints
Days 23-29: 24,36,48,60,72,84,96,108, 120,144 and 168 hr post Day 22 dose	±10 minutes

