9.7 Analysis of Exploratory Endpoints

Exploratory Endpoints will be summarized as follows (only subjects with primary hypothyroidism will be considered for the non-PK exploratory endpoints):

Endpoint	Applicable to	Timespan	Analysis Method
Observed Values	T4 fT4 TSH	Titration Period Maintenance Period	
Summarized by each protocol-specified timepoint using descriptive statistics (n, mean, SD, median, minimum, and maximum).
 
A line plot of the mean observed value will be provided over duration of the study.
 
A spaghetti plot with each subject compiled will be provided over the duration of the study for fT4 and TSH.
 
Repeat analysis using the Completer Population

Endpoint	Applicable to	Timespan	Analysis Method
Change from Baseline	T4 fT4 TSH	Titration Period Maintenance Period	
Summarized by each protocol-specified timepoint using descriptive statistics (n, mean, SD, median, minimum, and maximum).
 
A line plot of the mean change from baseline will be provided for each period.
 
Repeat analysis using the Completer Population

Total Plasma Concentrations	T4 T3	168-hr PK Period for Subjects in PK sub-study	
Summarized by collection timepoint and period using descriptive statistics (N, mean, SD, SD, %CV, median, minimum, maximum, geometric mean, and geometric %CV).
 
A line plot with mean and SD of concentrations by timepoint will be provided along with a by subject plot of concentration by timepoint.

t_{max} (hours)	T4 T3	168-hr PK Period for Subjects in PK sub-study	Summarized using descriptive statistics (n, mean, SD, %CV, median, minimum, maximum, geometric mean, and geometric %CV).
C_{max} (ng/mL)	T4 T3	168-hr PK Period for Subjects in PK sub-study	Summarized using descriptive statistics (n, mean, SD, %CV, median, minimum, maximum, geometric mean, and geometric %CV).
$AUC_{0-168hrs}$	T4 T3	168-hr PK Period for Subjects in PK sub-study	Summarized using descriptive statistics (n, mean, SD, %CV, median, minimum, maximum, geometric mean, and geometric %CV).
Minimum Concentration (C_{min}) (ng/mL)	T4 T3	168-hr PK Period for Subjects in PK sub-study	Summarized using descriptive statistics (n, mean, SD, %CV, median, minimum, maximum, geometric mean, and geometric %CV).

Endpoint	Applicable to	Timespan	Analysis Method

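### The SAP's AUC formula is 0/0 when two adjacent concentrations after tmax are equal, and its geometric summaries of tmax fail if a predose value is the maximum: a minor defect in exploratory PK endpoints

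*SAP*

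**What the plan says.** SAP section 6.8 calls its AUC method linear-up log-down. It then defines it by a switch at tmax: linear before, and "the logarithmic trapezoidal method for all times after" tmax. The log term for an interval is (t_{i+1} − t_i)(C_i − C_{i+1}) / (ln C_i − ln C_{i+1}), with no exception for equal or rising pairs. Mean steady-state concentration is that AUC divided by 168 hours.

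The same section defines tmax as "Time in hours of the Maximum Value". It does not exclude predose and has no rule for tied maxima. In the AUC row, "The time 0 value will use the nominal time of collection at time 0". Protocol Table 5 schedules "Day 22: Predose" as a PK sample, followed by "Day 22: 1, 6, 12, and 18 hr post dose" and 11 further samples to 168 hours.

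For tmax of T4 and T3, SAP section 9.7 plans: "Summarized using descriptive statistics (n, mean, SD, %CV, median, minimum, maximum, geometric mean, and geometric %CV".

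No other section settles either case. SAP section 8.3 covers missing data and sets values below quantification to half the limit, which itself makes consecutive below-limit values equal. SAP section 10 allows SAS, R or Phoenix WinNonlin without saying which computes AUC or how ties are treated. Protocol section 13 lets the SAP prevail where methods differ.

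**The concern.** A stated calculation rule should give a value for every profile that the design can produce. This one does not. Two equal consecutive results after tmax leave one term of the sum undefined, and with it the subject's AUC and mean concentration. The programmer must then leave the value missing or choose an undocumented patch.

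The name and the definition also diverge. Under linear-up log-down, a rise after tmax is handled linearly and a fall before tmax logarithmically; under the written switch it is the reverse. Two programmers could code different algorithms from the same cell.

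For tmax, a predose maximum gives a time of 0. The planned geometric statistics must then be reported as undefined, reported as 0, or computed after dropping the subject, and the SAP does not say which.

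At stake are the T4 and T3 PK summaries in about 12 substudy subjects. The primary dose-conversion analysis uses neither AUC nor tmax.

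**Working it through.** The documents give no figure to reproduce here, so the check evaluates the SAP's formulas and then asks how often they fail.

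**1. Equal pair.** With C_i = C_{i+1} = C, the numerator is Δt × (C − C) = 0 and the denominator is ln C − ln C = 0. Setting C_{i+1} = C(1 − ε) gives Δt × Cε / (−ln(1 − ε)), which tends to Δt × C as ε goes to 0. That is the linear trapezoid. Example with C = 1.1 ng/mL and Δt = 12 h: the limit is 13.2 and the linear value is ½ × 12 × (1.1 + 1.1) = 13.2; direct evaluation returns not-a-number.

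**2. Rising pair after tmax.** Per unit time, starting from 1:
- 10% rise: linear (1 + 1.1)/2 = 1.0500; log 0.1/ln 1.1 = 1.0492; difference about 0.08%.
- 20% rise: linear 1.1000; log 0.2/ln 1.2 = 1.0970; difference about 0.28%.

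The mismatch with the named method is one of definition and has little numerical effect.

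**3. tmax of 0.** The geometric mean is exp(mean of ln t) and the geometric CV is √(exp(s²) − 1), with s the SD of ln t. One zero makes ln t = −∞, so s is undefined; the geometric mean is 0 by the product definition and undefined if computed from logs. In an illustrative set of 12 with one zero, the geometric mean is 0, or 34.3 h if the zero is dropped; the median is 36 h. If the actual predose clock time were used instead of nominal 0, it would be negative and its log still undefined.

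**4. Frequency.** From the documents: 5 + 11 = 16 samples, 15 adjacent pairs, about 12 subjects. Assumed, because the documents are silent: T3 near 1 ng/mL, CV 5-10%, and reporting resolution. Simulation used the protocol timepoints and the first occurrence of the maximum, and counted only ties after tmax, since earlier intervals are linear.

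| Flat T3, CV | Resolution (ng/mL) | Tie after tmax, per subject | At least 1 of 12 |
|---|---|---|---|
| 5% | 0.01 | 35% | 99% |
| 10% | 0.01 | 19% | 92% |
| 5% | 0.001 | 4% | 41% |
| 10% | 0.001 | 2% | 23% |

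The last column is 1 − (1 − p)^12; for p = 0.35, 1 − 0.65^12 = 0.994.

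For T4, the model was a one-compartment superposition with assumed half-life 7-9 days, single-dose peak at 24-48 h and a 400 µg dose, scaled from the mean Cmax of 27.6 ng/mL at 300 µg in protocol section 5.4.1.1. At least 1 of 12 has a tie after tmax with probability 97-100% at 1 ng/mL resolution, 31-60% at 0.1 and 4-8% at 0.01.

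For tmax = 0, a perfectly flat profile without ties gives 1/16 = 6.25% per subject, and 1 − (15/16)^12 = 53.9% for at least 1 of 12; rounding to 0.001 or 0.01 ng/mL gives 54-60%. With a true T3 peak-to-trough swing, at 0.01 ng/mL resolution:
- 5% swing: 21-34%
- 10% swing: 3-18%
- 20% swing: 0-3%

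For T4, with a modelled peak-to-trough ratio of 1.46-1.80, it is about 0%.

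**The case against.** A reader might infer that both failures are likely and that AUC would be missing for many T3 profiles. The documents do not support that. They contain no T3 profile, assay precision or reporting resolution, and the tie frequency runs from uncommon to near certain over plausible resolutions. A nearly flat T3 course is an outside premise. For T4, protocol section 5.4.1.1 reports a median Tmax about 30 hours later than oral or intravenous dosing, which makes a predose maximum very unlikely.

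The defence can go further. The singularity is removable, so the right value at a tie is not in doubt, and the software may already supply it. The log formula is valid for rising pairs and the switch at tmax is spelled out, so the method is reproducible apart from ties. Median, minimum and maximum of tmax are already planned, and the protocol synopsis calls for geometric statistics only where applicable. These endpoints are exploratory and descriptive.

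All of this limits the consequence. It does not remove the defect: the formula gives no value at a tie, no fallback is written, no program or tie option is assigned to AUC, and SAP section 9.7 lists the geometric statistics for tmax without qualification.

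**Conclusion.** Wrong as written, but minor. Three things follow from the text alone: the log rule is 0/0 for an equal pair after tmax, the definition is not the method it names, and the geometric summaries of tmax break down if any tmax is 0.

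How often this happens rests on assumptions. For a flat T3 profile with CV 5-10%, a tie after tmax occurs in about 19-35% of subjects at 0.01 ng/mL resolution (at least 1 of 12: 92-99%) and in about 2-4% at 0.001 ng/mL (at least 1 of 12: 23-41%). A tmax of 0 in at least 1 of 12 is about as likely as not (54-60%) only if T3 is perfectly flat; it falls quickly with any real peak and is about 0% for T4 under the modelled profile. Missing AUCs are therefore a possibility that depends on the assay and the software, not a demonstrated outcome.

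**What to change.** - **SAP section 6.8, AUC:** use the logarithmic trapezoid only for intervals where concentration strictly falls, and the linear trapezoid otherwise. This is linear-up log-down, and at a tie it equals the limit of the log formula.
- **SAP section 6.8, tmax:** take the first occurrence when maxima are tied.
- **SAP section 9.7, tmax:** report median, minimum and maximum, without geometric mean and geometric %CV.

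The cost is a few lines, with no new data. Areas shift slightly on rises after tmax and falls before it, by about 0.08% of the interval for a 10% change. If the sponsor prefers to keep the switch at tmax, a single clause applying the linear rule to equal pairs removes the 0/0 and changes no other value, but the method should then not be called linear-up log-down. Either choice should be fixed before the PK analysis is run.
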